6.5.7.4 Secondary Efficacy

6.5.7.4.1 Secondary Efficacy Analyses

The following secondary endpoints will be tested hierarchically:

- 1. CFB in Dryness Score (VAS scale) at Day 15
- 2. CFB in tCFS (NEI scale) at Day 15
- 3. CFB in VAS burning/stinging at Day 57
- 4. CFB in cCFS (NEI scale) at Day 57

Inference will only be made on these endpoints, at a 2-sided alpha = 0.05, if both primary endpoints and any higher order secondary endpoints are statistically significant at a 2-sided alpha = 0.05 in favor of NOV03.

Quantitative secondary efficacy endpoints will be summarized similarly to the primary efficacy endpoints.

The primary analysis of the secondary endpoints will use the FAS with available data per subject, assuming the overall study discontinuation rate is <5%. If the overall study discontinuation rate is $\ge5\%$, then the primary analysis of the secondary endpoints will be based on imputation methodology as defined in Section 6.5.7.3 and the available data analyses will become robustness analyses.

6.5.7.4.2 Other Pre-specified Efficacy Analyses

The other pre-specified efficacy analyses will use the FAS with available data per subject:

- 1. CFB of Dryness Score (VAS) at Day 29
- 2. CFB in tCFS at Day 29
- 3. CFB in CFS central and inferior sub-regions (NEI scale) to each measured postbaseline visit
- 4. Proportion of tCFS responders (≥3 improvement based on NEI scale) at Day 57
- 5. Proportion of Dryness Score responders (≥30% improvement from baseline) at Day 57
- CFB in VAS burning/stinging, sticky feeling, foreign body sensation, itching, blurred vision, sensitivity to light, pain, frequency of dryness, and awareness of dry eye symptoms at each measured post-baseline visit
- 7. CFB in OSDI at each measured post-baseline visit

Quantitative efficacy variables will be summarized descriptively (n, mean, standard deviation, median, min and max) by visit, and analyzed similarly to the primary endpoint at each measured visit. Least squares mean for each treatment group and for the difference between treatment groups will be presented from the model together with two-sided p-values and 95% confidence intervals. For assessments performed by eye, study eye and fellow eye will be summarized separately.

Endpoints evaluating the proportion of study eyes (or subjects) meeting pre-defined criteria will be presented and tested between treatment groups using logistic regression analysis adjusting for baseline tCFS score at each measured follow-up visit.

Sample SAS logistic regression code:

PROC LOGISTIC DATA=INDATA DESCENDING;
CLASS <TREATMENT
MODEL <ENDPOINT>=<TREATMENT> <BASELINE>;RUN;

Protocol Number: 904

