10.4.7 Other Pre-specified Efficacy Analyses

The analyses of other pre-specified endpoints will use the Full Analysis Set (FAS) with available data per subject.

1. CFB of Dryness Score (VAS) at Day 29.
2. CFB in tCFS at Day 29.
3. CFB in CFS central and inferior sub-regions (NEI scale) to each measured post-baseline visit.
4. Proportion of tCFS responders (≥ 3 improvement based on NEI scale) at Day 57.
5. Proportion of Dryness Score responders ($\geq 30\%$ improvement from baseline) at Day 57.
6. CFB in VAS burning/stinging, sticky feeling, foreign body sensation, itching, blurred vision, sensitivity to light, pain, frequency of dryness, and awareness of dry eye symptoms at each measured post-baseline visit.
7. CFB in Ocular Surface Disease Index (OSDI[®]) at each measured post-baseline visit.

Quantitative other pre-specified efficacy endpoints will be summarized descriptively (n, mean, standard deviation, median, min and max) by visit, and analyzed similarly to the primary endpoint at each measured visit. Least squares mean for each treatment group and

for the difference between treatment groups will be presented from the model together with two-sided p-values and 95% confidence intervals.

Two-sample t-tests, Wilcoxon rank sum tests and mixed-effect repeated measures analysis will also be presented as sensitivity analyses.

Other pre-specified endpoints evaluating the proportion of study eyes (or subjects) meeting pre-defined criteria will be presented and tested between treatment groups using logistic regression analysis adjusting for baseline tCFS score at each measured follow-up visit. Pearson chi-squared analysis comparing the treatment groups will be performed as sensitivity analyses.

Exploratory and other endpoints will be summarized and analyzed similarly to the other pre-specified endpoints.

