6.5.7.3 Primary Efficacy Analyses

The primary comparisons in this trial will be between NOV03 versus saline at Day 57 in the FAS with available data per subject using the following estimands

- Endpoint:
 - CFB in tCFS in the study eye at Day 57
 - CFB of Dryness Score (VAS) at Day 57
- Intercurrent event:
 - Discontinuation of study medications is ignored. [treatment policy strategy]
 - Non-optimal compliance is ignored. [treatment policy strategy]
 - Withdrawal due to any reason. Missing data not imputed. [hypothetical strategy if overall study discontinuation rate is <5%]
- Population-level summary:
 - Difference in the mean CFB in tCFS in the study eye at Day 57 between NOV03 and saline
 - Difference in the mean CFB of Dryness Score (VAS) at Day 57 between NOV03 and saline

If the overall study discontinuation rate in the FAS is \geq 5% then the primary analysis will be based on imputation methodology using the following estimands:

• Endpoint:

Protocol Number: 904

- CFB in tCFS in the study eye at Day 57
- CFB of Dryness Score (VAS scale) at Day 57

• Intercurrent event:

- Discontinuation of study medications is ignored. [treatment policy strategy]
- Non-optimal compliance is ignored. [treatment policy strategy]
- Withdrawal due to lack of efficacy or adverse events: baseline observation carried forward (BOCF) is used to impute missing data [hypothetical strategy if overall study discontinuation rate ≥5%]
- Missing data without withdrawal or withdrawal due to reasons other than lack of efficacy or adverse events: multiple imputations using randomized treatment-based Markov Chain Monte Carlo (MCMC) is used to impute missing data [hypothetical strategy if overall study discontinuation rate ≥5%]
- Population-level summary:
 - Difference in the mean CFB in tCFS in the study eye at Day 57 between NOV03 and saline
 - Difference in the mean CFB of Dryness Score (VAS scale) at Day 57 between NOV03 and saline

The primary comparison in this trial will be between NOV03 versus saline at Day 57. The primary efficacy endpoints (e.g. CFB in total corneal fluorescein staining [NEI scale] and Dryness Score) will be tested using hierarchical fixed sequence testing and summarized descriptively (n, mean, standard deviation, median, min, and max) and analyzed separately using an ANCOVA model with terms for baseline value, and treatment.

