6.5.8.2 Analysis Visits

The eCRF nominal study visits will be used for analysis. For subjects who withdraw from the study, if they withdraw at a regular scheduled visit, the data collected at the time of withdrawal will be summarized under the regular visit; if they withdraw between scheduled visits, the early termination visit will be treated as an unscheduled visit. For the purposes of table summarization, the first visit for each nominal study visit will be used.

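### If discontinuation reaches 5%, subjects who withdraw for lack of efficacy or adverse events count as zero change in the primary analysis but are missing from the Day 57 responder analyses of the same variables

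*SAP*

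**What the plan says.** **Responder endpoints.** SAP 6.5.7.4.2 lists "Proportion of tCFS responders (≥3 improvement based on NEI scale) at Day 57" and "Proportion of Dryness Score responders (≥30% improvement from baseline) at Day 57" among the other pre-specified endpoints. For all of these it says "The other pre-specified efficacy analyses will use the FAS with available data per subject". Protocol 10.4.7 agrees: "The analyses of other pre-specified endpoints will use the Full Analysis Set (FAS) with available data per subject". The protocol synopsis says the same. None of the three attaches a condition on the discontinuation rate.

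**Primary and secondary endpoints.** SAP 6.5.7.3 uses available data below 5% overall discontinuation and imputes at 5% or above. In that branch: "Withdrawal due to lack of efficacy or adverse events: baseline observation carried forward (BOCF) is used to impute missing data". Other missing values are filled by multiple imputation (MCMC) based on randomized treatment. The secondary endpoints follow: at 5% or above, "the primary analysis of the secondary endpoints will be based on imputation methodology as defined in Section 6.5.7.3".

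**Provisions that might bring the missing subjects back.**
- SAP 6.5.8.2 on early termination: "if they withdraw between scheduled visits, the early termination visit will be treated as an unscheduled visit". Such a visit does not supply a Day 57 value.
- SAP 6.5.8.6 leaves missing data as missing unless a rule is given.
- SAP 6.5.8.6.1 sends only the primary analysis to the imputation branch.
- SAP 6.5.7.6.3 gives a Pearson chi-squared test as the responder sensitivity analysis. That is a different test, with no stated change in how missing responses are handled.

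**The concern.** The plan has already decided how a subject who leaves for lack of efficacy or an adverse event is to be scored at Day 57 once discontinuation reaches 5%: no change from baseline. The responder analyses use the same variables at the same visit but do not follow that decision. The same subject is present with zero improvement in one table and absent from the next.

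A responder rate computed only in subjects with a Day 57 value is higher than one that counts these withdrawals as the primary analysis does. The between-arm difference can also shift. The responder proportions are compared by logistic regression, so p-values will be reported. Protocol 4.6 used responder results from the phase 2 trial to support the relevance of the changes seen there, so readers may well look at the present ones in the same way.

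**Working it through.** **1. Which branch the plan expects.** Inputs from SAP 6.5.10: 250 evaluable per arm, 10% discontinuation, 280 randomized per arm.
- 250 / (1 − 0.10) = 277.8, so 278, which the plan rounds to 280. The plan's figure reproduces.
- The 5% trigger is 0.05 × 560 = 28 subjects. The assumed discontinuation is 0.10 × 560 = 56 subjects, twice the trigger.

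The plan's own assumption therefore leads to the imputation branch. Available-data responder denominators would be about 280 × 0.90 = 252 per arm. The documents state no sample size, power or expected rate for the responder endpoints.

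**2. What carrying baseline forward implies.** The change is 0. Zero is below the 3-point improvement required for tCFS, and 0% is below the 30% required for Dryness Score. Under the primary rule such a subject is a non-responder on both.

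**3. Effect on the rates and the difference.** Let p be the responder rate in an arm among subjects with a Day 57 value, and w the number of withdrawals for lack of efficacy or adverse events without one. Subjects missing for other reasons are taken to respond at their own arm's rate p, roughly what treatment-based imputation would give.

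Rate with these withdrawals counted = p × (1 − w/280)

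This is below p whenever w > 0 and p > 0. The difference (NOV03 minus saline) changes by

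−(p_N × w_N − p_S × w_S) / 280

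It is unchanged when p_N × w_N = p_S × w_S, so what matters is the product of rate and count in each arm.

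Assumed values: p_N = 50%, p_S = 40%, and 28 such withdrawals in total (half of the 56).

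| w_N : w_S | NOV03 | Saline | Difference (points) |
|---|---|---|---|
| left out (as planned) | 50.0% | 40.0% | 10.0 |
| 14 : 14 | 0.50 × 266/280 = 47.5% | 0.40 × 266/280 = 38.0% | 9.5 |
| 20 : 8 | 0.50 × 260/280 = 46.4% | 0.40 × 272/280 = 38.9% | 7.6 |
| 8 : 20 | 0.50 × 272/280 = 48.6% | 0.40 × 260/280 = 37.1% | 11.4 |

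With a 12 : 15 split, 0.50 × 12 = 0.40 × 15 = 6.0, and the difference stays at 10.0 although the counts are unequal.

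**4. Check under a second set of assumptions.** Rates 40% and 30%, 28 withdrawals per arm, and other-reason withdrawals left missing throughout:
- As planned: 252 vs 252, difference 10.0 points, p = 0.019 (two-proportion z test).
- 14 such withdrawals in each arm: 37.9% vs 28.4% of 266 each, difference 9.5, p = 0.020.
- All 28 on NOV03, none on saline: 36.0% of 280 vs 30.0% of 252, difference 6.0, p = 0.14.
- None on NOV03, all 28 on saline: 40.0% of 252 vs 27.0% of 280, difference 13.0, p = 0.0015.

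The last two are extremes. Varying the rates from 35%/25% to 50%/40% moves them to between 6.5 and 5.0 points, and between 12.5 and 14.0 points; the balanced case stays at 9.5.

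**The case against.** The strongest reply is that this is deliberate tiering. Protocol and SAP agree that primary and secondary endpoints switch at 5% and that every other pre-specified endpoint stays on available data. The responder endpoints lie outside the alpha-controlled hierarchy. In the imputation branch the available-data analyses of the primary endpoints remain as robustness analyses, so a continuous result on the same basis as the responder tables will exist. Reasons for discontinuation are summarized by arm (SAP 6.5.1), so an imbalance would be visible. The SAP also labels the carry-forward rule "hypothetical strategy if overall study discontinuation rate ≥5" percent; it does not define these subjects as treatment failures. All of this stands and limits the weight of the point. It does not remove the mismatch between two tables of the same variable at the same visit.

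The scope is also narrow. Subjects who stop the drug may stay in the trial and are encouraged to attend later visits (Protocol 5.6 and 8.4.2), and those with a Day 57 value count in both analyses. Below 5% discontinuation the primary analysis uses available data too, so the mismatch does not arise.

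A reader might infer three stronger things that the documents do not support:
- *That the difference is biased whenever such withdrawals are unequal between arms.* The 12 : 15 split leaves it unchanged, and the equal 14 : 14 split moves it by half a point.
- *That the plan favors NOV03.* The shift can go either way, and the documents give neither responder rates nor withdrawal reasons by arm.
- *That every responder table could be rebuilt without any further imputation decision.* The sample imputation code (Protocol 10.4.3, SAP 6.5.7.3) covers only the five corneal regions, scored 0 to 3, and no Dryness Score model is written out. SAP 6.5.7.3 nevertheless requires imputed Day 57 values for both study-eye tCFS and Dryness Score, so that model is needed for the primary analysis anyway. Fellow-eye responder tables (14.2.9.2 and 14.2.9.4) have no such imputed values.

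**Conclusion.** The point holds as a consistency issue in supportive analyses, conditional on at least 5% overall discontinuation, which the plan's own 10% assumption implies. It concerns only subjects who withdraw for lack of efficacy or adverse events without a Day 57 value. Under the rule the primary analysis applies to them they are non-responders, so leaving them out raises the responder rate in any arm that has such subjects.

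The effect on the difference is about half a point when these withdrawals are balanced. In the assumed 20:8 and 8:20 splits it is about 2.4 points down or 1.4 points up. Fully one-sided splits give differences of about 5 to 14 points in place of 10. Responder rates, the share of withdrawals for these reasons and their split by arm are all assumptions. No primary or secondary conclusion and no type I error claim is affected. This is a cheap improvement rather than a necessary correction.

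**What to change.** In SAP 6.5.7.4.2 and Protocol 10.4.7, add that when overall discontinuation is 5% or more:
- Day 57 responder status for study-eye tCFS and for Dryness Score is derived from the same imputed Day 57 values that SAP 6.5.7.3 requires for the primary analysis: baseline carried forward for withdrawals due to lack of efficacy or adverse events, MCMC imputation for the rest.
- The logistic regression is run in each imputed dataset and the estimates are pooled.
- The available-data responder tables are kept as supportive. Fellow-eye tables may stay on available data.

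The Dryness Score imputation model should be written out at the same time, since the primary analysis needs it in any case.

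The cost is a sentence or two of text, modest programming, and slightly lower reported responder rates. The change should be made before database lock and unmasking; under SAP section 4, a version added later and not pre-planned would have to be reported as post hoc.

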6.4.1.3 Other Pre-specified Efficacy Endpoints

- 1. CFB of Dryness Score (VAS) at Day 29
- 2. CFB in tCFS at Day 29
- 3. CFB in CFS central and inferior sub-regions (NEI scale) to each measured postbaseline visit
- 4. Proportion of tCFS responders (≥3 improvement based on NEI scale) at Day 57
- 5. Proportion of Dryness Score responders (≥30% improvement from baseline) at Day 57

- CFB in VAS burning/stinging, sticky feeling foreign body sensation, itching, blurred vision, sensitivity to light, pain, frequency of dryness, and awareness of dry eye symptoms at each measured post-baseline visit
- 7. CFB in OSDI at each measured post-baseline visit

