6.5.8.5 Adjustment for Covariates

The primary endpoints are CFB in total corneal fluorescein staining (NEI scale) at Day 57 and CFB of Dryness Score (VAS) at Day 57. The two primary endpoints will be analyzed separately using an ANCOVA model with baseline measurement as a numeric covariate and treatment as the main effect.

Subject randomization is stratified by clinical site and dryness score $<70 \text{ vs} \ge 70 \text{ (VAS)}$ at baseline (Visit 1). The analyses will not be adjusted for the stratification factors.

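### The Dryness Score responder model adjusts for baseline corneal staining, not baseline Dryness Score: a small mismatch with the primary Dryness model that is free to correct

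*SAP*

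**What the plan says.** SAP 6.5.7.4.2 gives one model for every responder endpoint. The sentence opens with "Endpoints evaluating the proportion of study eyes (or subjects) meeting pre-defined criteria" and says that they are tested by logistic regression "adjusting for baseline tCFS score at each measured follow-up visit". Protocol 10.4.7 carries the same rule ("logistic regression analysis adjusting for baseline tCFS score at each measured follow-up visit"), and so does the statistical part of the protocol synopsis (section 1.2).

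Two responder endpoints are visible in the unredacted text: tCFS responders, and "Proportion of Dryness Score responders (≥30% improvement from baseline) at Day 57". Dryness is scored once for both eyes together (SAP 6.5.4.1.1), so it is the only visible endpoint to which the bracketed mention of subjects can refer. The tCFS rule therefore reaches it.

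For the primary endpoints, SAP 6.5.8.5 specifies a separate ANCOVA for each, "with baseline measurement as a numeric covariate and treatment as the main effect". The mixed model in SAP 6.5.7.6.1 also carries the baseline value. SAP 6.5.8.5 adds that randomization is stratified by site and by baseline Dryness (below 70 versus 70 or more), and that the analyses do not adjust for these factors. It does not mention the responder models.

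The sample logistic code in SAP 6.5.7.4.2 reads "MODEL <ENDPOINT>=<TREATMENT> <BASELINE>;RUN". The placeholder is not defined.

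**The concern.** The covariate fits one of the two responder endpoints and looks carried over to the other. A Dryness response is defined relative to baseline Dryness, and the trial considered baseline Dryness important enough to stratify on. Yet no visible analysis of Dryness responders adjusts for it: the logistic model uses tCFS, the sensitivity analysis is an unadjusted chi-squared test (SAP 6.5.7.6.3), and the stratification factors are left out.

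Text and code can also diverge. The ANCOVA code in SAP 6.5.7.3 uses the same `<BASELINE>` placeholder, and there it means the endpoint's own baseline. A programmer who follows the code by analogy would enter baseline Dryness; one who follows the sentence would enter baseline tCFS. A prespecified endpoint should not have two defensible results.

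What is at stake is interpretive. Protocol 4.6 uses phase 2 responder analyses to support the relevance of the observed changes. A responder result used in that way is best matched to the primary Dryness model.

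**Working it through.** **1. The adjusted models side by side**

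| Analysis | Baseline covariate |
|---|---|
| tCFS change, ANCOVA and mixed model | tCFS |
| Dryness change, ANCOVA and mixed model | Dryness |
| tCFS responder, logistic | tCFS |
| Dryness responder, logistic | tCFS by the text; unspecified in the code |

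Only the last row departs from the pattern.

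**2. The plan's own figures.** The documents give no responder rate or power for this endpoint. The inputs that they do give (Protocol 10.3) are 250 per arm, a Dryness difference of -10, SD 28 and two-sided alpha 0.05. SE = 28 × √(2/250) = 2.504; 10/2.504 = 3.993; 3.993 - 1.960 = 2.033; Φ(2.033) = 97.9%, as stated. The tCFS ratio 1.0/2.8 is the same as 10/28, so the joint power under independence is 0.979 × 0.979 = 95.8%, also as stated. These figures confirm the inputs but do not test the covariate.

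**3. Effect of the covariate.** Simulation with 3,000 trials per row, 250 per arm, randomization balanced within Dryness below 70 and 70 or more.

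Assumptions not in the documents:
- baseline Dryness about normal, mean 65, SD 20;
- mean change on saline -20;
- baseline tCFS unrelated to Dryness response;
- slope of Dryness change on baseline Dryness varied from 0 to -0.8;
- SD 28 taken as the total within-arm SD of change.

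Simulated responder rates were about 51% on saline and 64% to 66% on NOV03.

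| Slope | Correlation of response with baseline Dryness | Power, tCFS-adjusted | Power, Dryness-adjusted | Odds ratio, tCFS-adjusted | Odds ratio, Dryness-adjusted |
|---|---|---|---|---|---|
| 0 | -0.16 | 87.6% | 88.2% | 1.76 | 1.79 |
| -0.25 | -0.03 | 89.1% | 89.3% | 1.80 | 1.81 |
| -0.5 | 0.11 | 91.1% | 91.3% | 1.84 | 1.86 |
| -0.8 | 0.30 | 95.0% | 96.3% | 1.91 | 2.05 |

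The power gain is 0.2 to 1.3 points. A model with no covariate gave 87.7%, 89.2%, 91.2% and 95.1%, so under these assumptions adjusting for tCFS amounts to no adjustment. With stratification switched off at slope -0.8, the powers were 93.8% and 95.9%, a gap of 2.1 points.

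**4. Type I error** (no treatment effect; slopes 0, -0.5, -0.8): 4.7%, 5.4%, 3.6% with tCFS and 4.8%, 5.2%, 4.4% with Dryness. The Monte Carlo SE near 5% is √(0.05 × 0.95/3000) = 0.4 points, so neither covariate shows inflation.

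**5. Stress case.** A direct logistic model, unstratified, with a conditional odds ratio of exp(0.5) = 1.65. As the log odds ratio per SD of the omitted baseline rises from 0 to 1.0, power without it falls from 79.4% to 65.2%, against 79.3% to 73.0% with it. The largest loss is 73.0 - 65.2 = 7.8 points. The average odds ratio without the baseline falls from 1.65 to 1.52, while with it the odds ratio stays at 1.65.

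**The case against.** The rule is prespecified and the same in all three places, and a valid randomized comparison does not need the best covariate. Baseline Dryness is not shown to be prognostic: a percentage-change response is already scaled to baseline, and the simulated correlation ran from -0.16 to +0.30, so the association could be weak or of either sign. Stratification limits imbalance in baseline Dryness to what remains within strata. The chi-squared test gives a result that does not depend on tCFS. The endpoint is not in the testing sequence of Protocol 10.4.4 or SAP 6.5.8.9. All of this stands, and it is why the point is minor.

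A reader might infer more than the documents support:
- *That the responder result would be biased or invalid.* Type I error is not inflated. The move from 1.91 to 2.05 is a difference between two conditional odds ratios, which arises from non-collapsibility even with perfect randomization.
- *That tCFS is unrelated to Dryness.* Independence is only a working assumption for power, and Protocol 10.3 itself mentions possible positive correlation.
- *That every continuous analysis uses its own baseline.* The t-tests and Wilcoxon tests use none; the statement holds for the ANCOVA and mixed models.
- *That the odds ratio cannot be read alongside the primary Dryness result.* The scales differ whichever covariate is used. The responder model is simply not matched to the primary one.

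What the objection does not answer is why the Dryness responder model alone should use another endpoint's baseline, or which variable the code's placeholder means.

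**Conclusion.** The mismatch is real and minor. Read literally, the Dryness responder model adjusts for baseline tCFS and omits baseline Dryness, and the code leaves the choice open. Under the main assumed inputs, using baseline Dryness changes power by about 0 to 1 point and moves the odds ratio away from 1 by up to 2.05/1.91 - 1 = 7%. The stress case reaches about 8 points of power and 1.65/1.52 - 1 = 9%, but it needs a prognostic strength that the documents do not establish. Baseline Dryness is presumed prognostic; its use as a stratification factor is the only support in the text. The assumed baseline distribution and saline response affect the levels, and SD 28 may be nearer a residual SD, since the synopsis derives its source estimates from an ANCOVA. No confirmatory claim is affected.

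**What to change.** In the protocol synopsis (1.2), Protocol 10.4.7 and SAP 6.5.7.4.2, replace the covariate phrase with: *adjusting for the baseline value of the corresponding endpoint (baseline tCFS for tCFS responders, baseline Dryness Score for Dryness Score responders)*. In the SAP's PROC LOGISTIC example, define `<BASELINE>` in the same terms. Change all three places together, since editing only some of them would create a contradiction. If the protocol is not reissued, record the change in SAP 6.6, which at present lists none.

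The cost is one phrase in three places and one code note. Baseline Dryness is already collected at Visit 1 and used in the primary model. The change should be made before unmasking, because choosing between text and code afterwards would look post hoc. The chi-squared analysis can stay as it is.
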